3. STATISTICAL METHODS

3.1 General

All data will be analyzed using the Statistical Analysis System (SAS®; Version 9.2 or higher).

Continuous variables will be presented by descriptive statistics: n, mean, standard deviation, median, minimum, and maximum. Categorical variables will be tabulated by frequency count and percentage. No hypothesis testing will be performed.

3.1.1 *Display of Decimal Places*

Means and medians will be reported to one decimal place more than the original unit reported on the case report form (CRF) or by the laboratory/vendor. Standard deviations will be reported to two decimal places more than the original unit. Minimum and maximum values will be reported to the same number of decimal places displayed on the CRF or by the laboratory/vendor.

3.1.2 *Visit Windowing*

For Vital signs, ECG, Lab and physical exam, the following protocol-specified visits are further defined for summary tables as below.

- Screening Visit (Baseline): the day subject was screened following the ICF signing
- Follow-up visit (3 Months): the visit date was most close to 91 days after baseline visit.
- Follow-up visit (6 Months): the visit date was most close to 183 days after baseline visit.
- Follow-up visit (9 Months): the visit date was most close to 274 days after baseline visit.
- Follow-up visit (12 Months): the visit date was most close to 365 days after baseline visit.
- Follow-up visit (15 Months): the visit date was most close to 456 days after baseline visit.
- Follow-up visit (21 Months): the visit date was most close to 640 days after baseline visit.
- Follow-up visit (27 Months): the visit date was most close to 822 days after baseline visit
- Follow-up visit (33 Months): the visit date was most close to 1005 days after baseline visit
- Follow-up visit (39 Months): the visit date was most close to 1187 days after baseline visit

For completed subjects, Follow-up visit (39 Months) is considered End of study visit.

For discontinued subjects, if the assessments at the scheduled visit prior to the early termination (ET) visit were not done, the ET visit will be assigned as the prior scheduled visit. Otherwise, the ET visit will be assigned to the next scheduled visit.

Other visits will be listed as “Unscheduled Visits”, and data collected at unscheduled visits will not be included in the summary table, but will be presented in the data listings.

3.1.3 *Missing Data Handling*

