In general, all categories that appear on the CRF and in summary table templates will be reported even if no patients reported that category (e.g., if there are no patients of a particular race). The “Missing” category displayed for categorical variables in summary table templates will only be displayed if missing observations are present. If no observations meet the criteria for inclusion in a data display (e.g., if there are no SAEs), the table or listing will be generated with a line in the body of the listing such as “None reported.”

No imputation will be conducted for the missing data.

3.1.4 *Sub-group Analyses*

All safety endpoints will be analyzed by MG type: MuSK-MG and AChR-MG.

3.2 *Subject Disposition, Demographics, Baseline Characters and Study Drug Compliance*

3.2.1 *Patient Disposition*

Study completion status will be summarized for all patients. The duration of treatment will be summarized for treated patients. Categories summarized will include patients who were planned, screened, screen failure, enrolled, received study drug, completed the study, were lost to follow-up, or withdrew early. Reasons for screen failure and withdrawal will be summarized.

3.2.2 *Protocol Deviations*

Individual protocol deviations will be presented in a data listing.

3.2.3 *Demographics and Baseline Characters*

Demographic characteristics of all patients enrolled will be summarized descriptively. The summary will include age, gender, race/ethnicity, height, weight.

3.2.4 *Study Drug Exposure*

The treatment duration (day), the total dose (mg) of study drug administered, average daily dose of study drug, and study drug compliance (%) will be tabulated.

- Treatment Duration (day) is calculated as The Last Dose Date – The First Dose Date +1. If the last dose date is missing, then the last visit date will be used.
- Total Dose (mg) will be calculated as the sum of the daily dose (mg) over the Treatment Duration, considering different doses during individual time periods within the study, as documented in the IP Accountability eCRF page.
- Average Daily Dose (mg) will be calculated as Total Dose (mg) / Treatment Duration (day). This will be calculated considering each time period and Daily dose during that period, as documented in the IP Accountability eCRF page.
- Study Drug Compliance (%): $100 \times \text{Total Dose Taken (mg)} / \text{Total Dose Prescribed (mg)}$

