3.5 Key Data Items

Study Analysis Population Definition:

- All Subjects: All subjects, including screening failures, who provided clinical information in the database.
- Safety Population: All enrolled subjects who receive at least one dose of study drug.

Important Derived Variables:

- Age (in year) = (Screening Date – Date of Birth +1)/365.25.
- Prior Medications and Treatments: The medications and treatments started before enrolled to the study (date of Informed Consent signed)
- Concomitant Medication and Treatments: The medications and treatments started on or after the date of Informed Consent signed
- Baseline: All safety measurements collected at Day 1 or before the first dose of study drug will be used as baseline
- Post Baseline Visit: follow up visit of 6, 9, 12, 15, 21, 27, 33 and 39 months after baseline and etc, or unscheduled visit after first dose of the study drug
- Study Day for follow-up visit: The visit date – Baseline date +1
 - o Follow-up visit at 3 months: The visit that is closest to study day 91
 - o Follow-up visit at 6 months: The visit that is closest to study day 183
 - o Follow-up visit at 12 months: The visit that is closest to study day 365
 - o Follow-up visit at 15 months: The visit that is closest to study day 456
 - o Follow-up visit at 21 months: The visit that is closest to study day 640
 - o Follow-up visit at 27 months: The visit that is closest to study day 822
 - o Follow-up visit at 33 months: The visit that is closest to study day 1005
 - o Follow-up visit at 39 months: The visit that is closest to study day 1187
- Duration of Disease (year):
(Date of Informed Consent signed – Date of original Diagnosis +1) / 365.25
- Study drug compliance (%): $100 \times \text{Total Dose (mg)} / \text{Total Prescribed Dose (mg)}$, where total dose taken will be calculated as (Dispensed # - Retuned # - Lost #) $\times 10$ mg (refer to CRF IP Accountability page (DA domain), and the total prescribed dose is collected at each IP accountability CRF (EX domain))
- Treatment emergent Adverse Events (TEAE): All AEs reported in this study are TEAE

Formulas of Metric Conversion:

- 1 inch = 2.54 cm
- 1 lb = 0.4536 kg
- $^{\circ}\text{C} = (^{\circ}\text{F} - 32) \times 5/9$

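### The SAP's closest-visit rule has no maximum distance and no use-once condition, and its two target lists disagree on Month 9, so the by-visit safety tables are not uniquely defined

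*SAP*

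**What the plan says.** - **SAP 3.1.2 (Visit Windowing)** covers vital signs, ECG, laboratory and physical examination data and says that "the following protocol-specified visits are further defined for summary tables as below". It gives nine targets, counted in days after baseline: 91, 183, 274, 365, 456, 640, 822, 1005 and 1187. Each has the same form, such as "Follow-up visit (9 Months): the visit date was most close to 274 days after baseline visit" and, for Month 39, "the visit date was most close to 1187 days after baseline visit".
- **The same section** places an early-termination (ET) visit in the preceding scheduled slot if that visit was not done, and in the following slot otherwise. Remaining visits are treated as unscheduled and appear only in listings.
- **SAP 3.1.3** states "No imputation will be conducted for the missing data". The protocol synopsis (Safety Analysis) likewise restricts the safety analysis to observed data.
- **SAP 3.5 (Key Data Items)** repeats the rule on a study-day scale, which adds 1 to the difference in dates. Its list has eight targets and goes straight from "Follow-up visit at 6 months: The visit that is closest to study day 183" to "Follow-up visit at 12 months: The visit that is closest to study day 365". Yet the line above it reads "Post Baseline Visit: follow up visit of 6, 9, 12, 15, 21, 27, 33 and 39 months after baseline", which names Month 9 and leaves out Month 3.
- **SAP 3.3** plans by-visit summaries at all nine visits. Protocol Table 1 schedules visits within 1 week either side, but the SAP does not adopt this as an analysis window.

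**The concern.** A rule that asks which visit is closest always returns an answer if the patient has any follow-up visit. With no distance limit and no use-once condition, an empty slot is filled by whichever visit happens to be nearest, however far away. For a patient who has stopped, that is the last visit, repeated to Month 39. The count at late visits would then be the number of patients ever followed up, not the number seen at that time, and old values would be presented as long-term data. Late visits carry most of the information on the study's primary objective, and early stopping is foreseeable because planned participation is only at least 9 months.

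The two target lists also differ, and nothing in the SAP says which governs. Two programmers could follow the text in good faith and produce different counts, means and shift tables.

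**Working it through.** **1. The plan's own targets.** Target = months × 365.25/12. For 3, 6, 9, 12, 15, 21, 27, 33 and 39 months this gives 91.3, 182.6, 273.9, 365.3, 456.6, 639.2, 821.8, 1004.4 and 1187.1. All nine targets in 3.1.2 agree within 1 day. The targets are sound; the assignment rule is the problem.

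**2. Literal reading: each target picks its closest visit.**

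| Patient's visits (days after baseline) | Later slots filled, 3.1.2 | Later slots filled, 3.5 |
|---|---|---|
| 91 only | Months 6–39: 8 | Months 6, 12–39: 7 |
| 91, 183 | Months 9–39: 7 | Months 12–39: 6 |
| 91, 183, 274 | Months 12–39: 6 | Months 12–39: 6 |

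Carry-forward therefore occurs with or without a Month 9 target.

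**3. Month 9 under the 3.5 list, literal reading.** Suppose a patient attends Months 6, 9 and 12, each within 7 days of target. The Month 6 visit is at most 7 days from 183, while the earliest Month 9 visit (day 267) is 267 − 183 = 84 days away. The same holds on the Month 12 side: 365 − 281 = 84. Over all 15 × 15 × 15 = 3375 combinations of shifts, the Month 9 visit is selected for Month 6 or 12 in none. It simply has no slot. It enters another slot only when a visit is absent, for example Month 12 after stopping at Month 9.

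**4. Month 9 under the 3.5 list, opposite reading: each visit picks its closest target.** Study days 267–273 go to Month 6 and study days 275–281 go to Month 12. Study day 274 is a tie, since 274 − 183 = 91 and 365 − 274 = 91. This reading produces no carry-forward.

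**5. Ties and day count.** Under 3.1.2, if Month 12 is missed, days 274 and 456 are both 91 days from 365, and there is no tie rule. If Month 6 is missed, day 274 is 91 days from 183 and day 91 is 92 days away, so the Month 9 visit is picked. On the 3.5 scale the same two visits are study days 275 and 92, at distances 92 and 91, so the Month 3 visit is picked. The one-day difference matters only in near-ties like this. The smallest half-gap between the nine targets is 91/2 = 45.5 days, far more than 7 + 1 = 8.

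**6. ET rule.** Month 15 is completed at day 456 and the ET visit falls one week later, at 456 + 7 = 463. The rule sends it to Month 21, which is 640 − 463 = 177 days from the target.

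**7. After bounding.** Midpoints of adjacent targets are 137, 228.5, 319.5, 410.5, 548, 731, 913.5 and 1096. With these limits, a patient seen at days 91 and 183 fills Months 3 and 6 only, day 274 falls in Month 9, and day 463 falls in Month 15.

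**The case against.** The best defence is to read the SAP as a whole. Section 3.1.2 is the windowing section for the summary tables, it lists Month 9, and 3.3 reports Month 9, so the gap in 3.5 looks like one dropped bullet. The no-imputation statement and the protocol's restriction to observed data both point away from carry-forward. The ET rule gives a discontinued patient's final visit a single slot, which would be pointless if one visit could fill every later slot. This makes carry-forward unlikely to be the intent.

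It does not settle the matter. No sentence bars an ordinary last visit from being closest to later targets, and the ET rule covers only ET visits. The protocol cannot override the SAP wording, because protocol 13.7 lets the SAP prevail where the two differ.

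The defence is right on three lesser points:
- Month 3's absence from the post-baseline line is minor. That line is open-ended, and 3.5 gives Month 3 its own target.
- The one-day difference in counting cannot move an on-schedule visit when all nine targets are used.
- Midpoint limits and a particular tie rule are choices, not requirements.

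A reader might also infer that the rule carries dropouts forward and, at the same time, routinely files Month 9 data under Months 6 and 12. The documents do not support both at once. The first needs targets to pick visits and the second needs visits to pick targets (steps 2 to 4). Nor is Month 9 undefined throughout the SAP, since 3.1.2 defines it.

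**Conclusion.** Wrong as written; low-to-moderate importance. The visit rule lacks a bound and a use-once condition in both sections. Taken literally, it repeats a Month 6 dropout's last visit at seven later targets (3.1.2) or six (3.5), contrary to the SAP's own missing-data statement. The Month 9 gap in 3.5 is a separate internal inconsistency. The ET rule can mislabel a visit by about six months.

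The exposure is nine of the 18 planned tables: T11–T17, T19 and T20. All are descriptive, and no hypothesis is tested. One might infer that the primary adverse-event results are affected; they are not, because T06–T10 count patients with events and use no visit windows.

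The carry-forward figures assume that each target picks its closest visit and that no ET visit is recorded. The documents give no expected dropout rate, so the number of patients affected cannot be stated.

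**What to change.** Replace the lists in 3.1.2 and 3.5 with one table, in days after baseline, and have 3.5 refer to it. For example, using the midpoints above and giving boundary days to the earlier visit:

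| Visit | Target | Window |
|---|---|---|
| Month 3 | 91 | stated lower limit to 137 |
| Month 6 | 183 | 138–228 |
| Month 9 | 274 | 229–319 |
| Month 12 | 365 | 320–410 |
| Month 15 | 456 | 411–548 |
| Month 21 | 640 | 549–731 |
| Month 27 | 822 | 732–913 |
| Month 33 | 1005 | 914–1096 |
| Month 39 | 1187 | 1097 to stated upper limit |

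Add these rules:
- One record per patient per window, the one closest to target, with a stated tie rule.
- Each visit is used at most once.
- Empty windows stay missing.
- One day count throughout.
- ET visits are placed by the same windows.
- Whether an unscheduled visit may fill a window; 3.5 counts such visits as post-baseline, while 3.1.2 keeps them out of the tables.

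Other bounded limits would serve equally well if fixed in advance. One consequence should be accepted knowingly: an ET visit that shares a window with a completed scheduled visit may then appear only in listings, unless a separate last-visit row is added.

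The cost is one SAP table and a few sentences. No new data are needed and, under protocol 13.7, no protocol amendment.

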3.6 Change to Planned Protocol Analysis

In a randomized, placebo-controlled MSK-002 study, amifampridine phosphate was not effective in demonstrating a difference over placebo in MG-ADL score change from Day 0 (Baseline) to Day 10. Based on the sponsor decision, no statistical analysis will be conducted for the efficacy endpoint, change from baseline in MG-ADL score.

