13.4 Secondary Endpoint

The secondary endpoint of the study is the MG-ADL score at Months 3, 6, 9, 12, 15, 21, 27, 33 and 39.

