1. INTRODUCTION

1.1 Objectives

The present long-term extension study will evaluate safety and tolerability of amifampridine on clinical laboratory test variables, ECGs, AEs, vital signs, physical examinations and the effects on MG-ADL score over several months in patients with MuSK-MG or AChR-MG. is needed to demonstrate that the product is safe and in patients with MG.

- The primary objective of the study is to evaluate the long-term safety and tolerability of amifampridine in patients with MuSK-MG; and with AChR-MG.
- The secondary objective of the study is to assess the effect of amifampridine phosphate on Myasthenia Gravis Activities of Daily Living Score (MG-ADL).

This Statistical Analysis Plan (SAP) corresponds to the Statistical Approach section of Clinical Protocol MSK-003, amendment, dated February 07, 2020, with additional changes included to the Version 1.0 dated 25 Oct 2022.

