1.2 Design

The study will enroll those patients who have completed the MSK-002 study and after all final evaluations for that study have been completed, or those who demonstrated benefit after completing the dose titration period but failed to meet the randomization criteria on Day 0 of MSK-002.

The duration of participation for each patient is expected to be at least 9 months as patients may continue in the study until amifampridine is approved by Regulatory Agencies or the clinical development of amifampridine is terminated for this indication. In addition to amifampridine, patients will continue to receive previous concomitant medications, as needed.

After a new informed consent is signed and inclusion / exclusion criteria for the current protocol are satisfied, eligible patients will be given the optimal dose and dosing schedule that was identified in the Run-in Period from Protocol MSK-002.

The findings from the physical exam (including vital signs, weight); 12-lead ECG; clinical laboratory test results (including pregnancy testing) and any ongoing adverse events will be used as the baseline for the long-term safety evaluation.

The only efficacy measurement is the MG-ADL which will be completed every 3 or 6 months. Safety and tolerability assessments will be made every 3 or 6 months or more frequently at the discretion of the Investigator. The study will continue until amifampridine is approved by Regulatory Agencies or until development of the product for this indication is halted or until month 39 is reached. The Investigator may alter the dose and dosing frequency during the Long-Term Study as well as schedule additional clinic visits for any reason.

Patients will be seen in the clinic at the end of Months 3, 6, 9, 12, 15, 21, 27, 33 and 39. In between the 3-or 6-month visits, patients may also have telephone/video contact with the site, or unscheduled visits, if needed.

Any unused medication must be brought back to the clinic at each visit for drug accountability, and an additional supply will be dispensed.

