2.2 Study Endpoints

2.2.1 *Safety Endpoint*

Safety endpoints of this study are:

- Incidence of patients experiencing treatment-emergent adverse events (TEAEs)
- Incidence of patients experiencing study drug-related TEAEs
- Incidence of patients experiencing equal or greater than Grade 3 TEAEs
- Incidence of patients discontinuing from the study due to TEAEs
- Physical exam and weight
- Vital signs including systolic blood pressure (SBP) and diastolic blood pressure (DBP), heart rate, respiration, and body temperature
- Clinical laboratory tests, including hematology, chemistry and urinalysis
- Concomitant medication review
- Electrocardiogram (ECG) parameters

2.2.2 *Efficacy Endpoint*

Efficacy endpoint of this study is change in MG-ADL score over time.

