2.3 Sample Size

The study is not powered with respect to any endpoint, but is an observational study to assess long term safety and lack of tolerance to the effects of amifampridine on MG-ADL. No sample size power calculation was conducted for this study.

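### SAP 3.6 cancels the MG-ADL analysis while the SAP keeps MG-ADL as its only secondary objective, and no planned table or listing includes it

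*SAP*

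**What the plan says.** **Protocol.** Section 7.2 gives one secondary objective, the effect on MG-ADL. Section 13.4 turns it into an endpoint: "The secondary endpoint of the study is the MG-ADL score at Months 3, 6, 9, 12, 15, 21, 27, 33 and 39". The synopsis (Efficacy Analysis) plans a descriptive summary of observed data, separately for MuSK-MG and AChR-MG, without pooling. Section 13.6 confirms that no hypothesis is tested.

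**SAP text that keeps MG-ADL.**
- 1.1 repeats the secondary objective and says the study will evaluate "the effects on MG-ADL score over several months in patients with MuSK-MG or AChR-MG".
- 1.2: "The only efficacy measurement is the MG-ADL which will be completed every 3 or 6 months".
- 2.2.2: "Efficacy endpoint of this study is change in MG-ADL score over time".
- 2.3 describes the trial as an "observational study to assess long term safety and lack of tolerance to the effects of amifampridine on MG-ADL".

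**SAP text that removes it.** Section 3.6 reports that in MSK-002 "amifampridine phosphate was not effective in demonstrating a difference over placebo in MG-ADL score change from Day 0 (Baseline) to Day 10", and then: "Based on the sponsor decision, no statistical analysis will be conducted for the efficacy endpoint, change from baseline in MG-ADL score". It gives no other reason.

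**The concern.** An objective, an endpoint and a stated purpose remain in the SAP with nothing behind them. Someone who programmed the SAP exactly as written would produce no output on the study's only secondary objective. Without a listing, a reader of the report could not reconstruct the result either.

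The timing also matters. A prespecified secondary endpoint, scheduled at every post-baseline visit, is dropped by sponsor decision after a negative result on the same scale in the parent trial. Even when disclosed, that invites the charge of selective reporting, and the plan has no output that would answer it.

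**Working it through.** The documents give no power, alpha or effect size on this point, so there is no figure of the plan's to reproduce. The check is a count of outputs, a count of the data concerned, and a comparison of the stated reason with the question asked.

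**1. Outputs that include MG-ADL**

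| Source | Items | Count | With MG-ADL |
|---|---|---|---|
| SAP 4.1 tables | T01–T03 (3) + T06–T17 (12) + T19–T21 (3) | 18 | 0 |
| SAP 4.2 listings | DL01–DL03 (3) + DL05 (1) + DL06a–d (4) + DL07–DL13 (7) + DL15 (1) | 16 | 0 |

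The gaps in the numbering (T04, T05, T18, DL04, DL14) do not show what, if anything, was removed, and nothing is inferred from them.

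**2. Supporting rules.** The visit windows in SAP 3.1.2 cover vital signs, ECG, laboratory tests and physical examination. The by-type rule in 3.1.4 covers safety endpoints, and the baseline definition in 3.5 covers safety measurements. None of these extends to MG-ADL. Read literally, 3.6 cancels only the analysis of change from baseline. That no MG-ADL analysis remains is an inference from 3.6 together with these gaps and the empty output lists.

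**3. Scheduled scores with no output.** Inputs: about 60 MuSK-MG and about 10 AChR-MG patients (protocol synopsis), and nine scheduled post-baseline visits, of which three fall by Month 9 (protocol Table 1). Scores = patients × visits.

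| Scenario | MuSK-MG | AChR-MG | Total |
|---|---|---|---|
| All stay only to Month 9 | 60 × 3 = 180 | 10 × 3 = 30 | 210 |
| Half leave after Month 9 (assumed) | 30 × 3 + 30 × 9 = 360 | 5 × 3 + 5 × 9 = 60 | 420 |
| All reach Month 39 | 60 × 9 = 540 | 10 × 9 = 90 | 630 |

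An early termination visit off the schedule adds at most one score per patient. For completers, SAP 3.1.2 treats Month 39 as the End of Study visit.

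**4. Reason against question.** The reason in 3.6 is a randomised comparison with placebo over 10 days. The question in SAP 1.1 and 2.3 is how MG-ADL behaves under continued open-label treatment, first measured at Month 3 and last at Month 39. The first result bears on whether there is an effect to maintain. It does not describe the later scores. Nor does it explain the missing listing, since a listing is not a statistical analysis. The endpoint in protocol 13.4 is the score at each visit, which 3.6 does not mention.

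**The case against.** The strongest reply is that the change is open and covered by a rule. It stands in a section on changes to the planned analysis, with its reason, and protocol 13.7 says the SAP prevails over the protocol's analysis text without an amendment. That stands as far as it goes: the departure from the protocol is not hidden. But the rule settles differences between the two documents. It cannot settle a conflict inside the SAP, and it does not withdraw the objective in protocol 7.2.

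A second reply is that little inference is lost. The study is open-label and uncontrolled, investigators may change dose and concomitant medication, and the parent trial was negative. This is right, and it limits what the data can show. It does not support leaving a stated objective with no output, because the protocol's plan was descriptive from the start.

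Three narrower points also stand. SAP 1.2 describes data collection and stays true under 3.6, so the real conflict is with 1.1, 2.2.2 and 2.3. The figure of 210 is not a lower bound, because patients may withdraw before Month 9. And a sponsor that wishes to keep its decision can remove the inconsistency with a listing and amended wording.

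**Conclusion.** The concern holds and should be fixed. Following the SAP as written leaves its only secondary objective unanswered: MG-ADL appears in 0 of 18 tables and 0 of 16 listings. Those two counts are the firm measure of size. The range of 210 to 630 scores is illustrative. It assumes full planned enrolment, no missed visits and no withdrawal before Month 9, and it counts scheduled assessments, not data collected. The middle case of 420 rests on an assumed dropout, since the documents give no rate. The primary safety analyses are not affected.

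**What to change.** **Preferred.** Replace the cancellation in SAP 3.6 with the protocol's descriptive plan:

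- Summarise observed MG-ADL score, and change from MSK-002 Day 0 (the baseline set in protocol 11.1), as n, mean, SD, median, minimum and maximum at Months 3, 6, 9, 12, 15, 21, 27, 33 and 39. Do this separately for MuSK-MG and AChR-MG, with no test and no pooling.
- Add one MG-ADL table to 4.1 and one listing to 4.2.
- Add MG-ADL to the windows in 3.1.2, still counted from the MSK-003 baseline visit, and to the by-type rule in 3.1.4. Name MSK-002 Day 0 in 3.5 as the MG-ADL baseline.
- Use the safety population, as SAP 2.1 already requires for all analyses. The synopsis would also require a post-treatment efficacy assessment. With observed data the difference touches only the baseline row and the denominator, because a patient with no later score enters no visit row.
- State three limits in the report. Day 0 follows dose titration, so it is not an untreated baseline. Comparability of the 30-day recall (protocol 8.7.1) with MSK-002 must be checked, because these documents do not give the MSK-002 recall period. Open-label, uncontrolled data can describe lack of tolerance but not establish it.

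Cost: SAP wording, one table and one listing, from data already scheduled for collection.

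**Fallback.** List the scores, mark in SAP 1.1, 2.2.2 and 2.3 that the objective will not be analysed, and give the reason in the report. Cost: SAP wording and one listing. Formally withdrawing the objective costs more: an amendment to protocol 7.2, for which protocol 13.7 requires IRB/IEC/REB approval before implementation.
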